13.2 Sample Size/Accrual Rate

The planned sample size for Cohort A is 25 patients and for Cohort B 10 patients. We anticipate accruing 1-2 patients per month in both Cohorts A and B.

13.3 Stratification Factors

The study will consist of two cohorts: Cohort A (*RAS MUT* patients) and Cohort B (*BRAF/RAS WT* patients).

13.4 Analysis of Secondary Endpoints

Cohort A (RAS MUT patients): One secondary endpoint will be to determine if treatment with trametinib can adequately increase iodine incorporation in thyroid cancer metastases to a threshold sufficient to warrant ^{131}I treatment in patients with RAI-refractory thyroid cancer. “Adequate increase” is defined as increasing iodine incorporation in thyroid cancer metastases to a predicted lesional absorbed radiation dose equal to or exceeding 2,000 cGy with the administration of \leq 300 mCi RAI. Proportion of patients with an adequate increase will be reported, along with the corresponding exact 95% confidence interval.

In another secondary analysis, the goal will be to determine whether treatment with trametinib and RAI is accompanied by decrease in thyroglobulin. For that purpose, we will perform a Wilcoxon signed rank test for paired samples to compare the thyroglobulin level before and after RAI treatment in the subset of patients treated with RAI.

Assessing the safety/tolerability of trametinib in combination with RAI will be investigated as a secondary endpoint. All patients will be evaluable for toxicity from the time of their first treatment with trametinib. Toxicities will be assessed through the NCI Common Terminology Criteria for Adverse Events version 4.0, individually reported and summarized. CTCAE version 5.0 will be utilized for AE reporting beginning April 1, 2018 but investigators may continue to collect and locally store AE data in CTCAE v4.0. Monitoring for trametinib-related toxicities will be continued until 30 days after the last dose of drug therapy.

Cohort B (BRAF/RAS WT patients): Secondary objectives will be determining the ORR (per RECIST v1.1 criteria) at the 6-month time point and the proportion of patients following at the 6-month time point alive without disease progression by RECIST v1.1 criteria (evaluation of these objectives will be conducted according to all the specific criteria described above in [Section 13.1](#) for Cohort A, including the allowance for patients to remain on study even with evidence of clinical or RECIST v1.1 radiologic disease progression prior to the 6-month time

point assessments).

In another secondary analysis, the goal will be to determine whether treatment with trametinib and RAI is accompanied by decrease in thyroglobulin. For that purpose, we will perform a Wilcoxon signed rank test for paired samples to compare the thyroglobulin level before and after RAI treatment in the subset of patients treated with RAI.

Assessing the safety/tolerability of trametinib in combination with RAI will be investigated as a secondary endpoint. All patients will be evaluable for toxicity from the time of their first treatment with trametinib. Toxicities will be assessed through the NCI Common Terminology Criteria for Adverse Events version 4.0, individually reported and summarized. CTCAE version 5.0 will be utilized for AE reporting beginning April 1, 2018 but investigators may continue to collect and locally store AE data in CTCAE v4.0. Monitoring for trametinib-related toxicities will be continued until 30 days after the last dose of drug therapy.

Cohort C (select patients from Cohorts A and B with insufficient ^{124}I PET changes): If analysis of the second lesional dosimetry suggests that therapeutic RAI will not be given, it will be concluded that the patient's cancer is still refractory to RAI and he/she will not receive RAI. Such patients may be continued on trametinib alone in Cohort C if 1) the treating physician determines it to be clinically reasonable, and 2) the patient agrees to continue on trametinib. The efficacy of MEK inhibition alone for RAI-refractory thyroid cancer has been evaluated with selumetinib in one phase II trial; that study reported only 1 partial response out of 32 evaluable patients. The study included only one patient with a *NRAS* Q61R MUT tumor and 11 patients with tumors wild-type for *BRAF*, *NRAS*, and *HRAS*. We hypothesize that more potent inhibition with trametinib will translate to greater clinical efficacy for patients with RAI-refractory thyroid cancers that are either *RAS* MUT or *BRAF/RAS* WT.

We estimate that approximately 10 patients in total from Cohorts A and B will be enrolled in Cohort C. Amongst these patients, we will estimate the proportion of patients following at the 6-month time point alive without disease progression by RECIST v1.1 criteria, the best objective response (BOR) along with the corresponding exact 95% confidence intervals, and the safety/tolerability of trametinib.

Changes in thyroglobulin will also be assessed while on treatment with trametinib; a Wilcoxon signed rank test for paired samples to compare the thyroglobulin level before and after RAI treatment in the subset of patients treated with RAI.

Exploratory Objectives: We will also be performing correlative studies on serial research biopsies in a minimum of 6 *RAS* MUT and 3 *BRAF/RAS* WT patients and archival tumor tissue in order to evaluate the impact of trametinib upon 1) expression and phosphorylation of MAPK signaling pathway proteins, 2) expression and phosphorylation of negative feedback loops connected to the MAPK pathway (such as her3), 3) quantitative levels of mRNA transcripts for MAPK regulated and thyroid-specific gene products, and 4) the presence of other genetic alterations (the studies and assays completed will be dependent upon the existing technology at the time of analysis as well as the funding that is available). These analyses will be descriptive and exploratory given the limited number of samples examined.

The impact of trametinib therapy upon RAI uptake and/or efficacy beyond one month is

unknown. Patients who do not receive ^{131}I after the second ^{124}I PET/CT and remain on trametinib (those on Cohort C) may be evaluated with a third ^{124}I PET/CT scan. These patients will have the same Cohort A and B primary/secondary endpoints evaluated in an exploratory manner. For patients who go on to be treated with ^{131}I , that data will not be included in the statistical analyses for Cohorts A and B, but kept separate for this exploratory analysis. The BOR data collected with trametinib therapy alone (prior to ^{131}I therapy) from these patients will still be used for Cohort C analysis.

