- h: chemistry includes albumin, alkaline phosphatase, total bilirubin, bicarbonate, BUN, calcium, chloride, creatinine, glucose, phosphorus, potassium, total protein, SGOT [AST], SGPT [ALT], sodium.
- i: The first research biopsy will be performed prior to initiation of Week 1 Day 1. The second biopsy will be performed in Week 3 of the study. It is preferred, but not required, that the second biopsy be performed upon the same tumor that was sampled with the first research biopsy, if safe and feasible. Patients may be exempt from biopsy if either the investigator or person performing the biopsy judges that no tumor is accessible for biopsy or that biopsy poses too great of a risk to the patient (if the only tumor accessible for biopsy is also the only lesion that can be used for RECIST v1.1 response evaluation, then the patient may be exempt from biopsy after discussion with the MSK Principal Investigator). Radiologic guidance (CT, MRI or ultrasound guided) approaches and obtaining multiple cores to ensure sufficient biopsy material (at least 3 cores preferred) are allowed as long as it is considered reasonably safe for the patient.
- j: beta-hcg (for women of childbearing potential) must be done within 2 days prior to administering ^{124}I .
- k: The days designated for these evaluations/tests are only suggestions. These can be scheduled for any time during the week for which they are scheduled.
- l: TSH, free T4, thyroglobulin, and thyroglobulin antibody will be drawn on Day 1 of weeks 1 and 5 (preferably prior to administration of Thyrogen on that day). Only TSH will be drawn on Day 3 during Weeks 1 and 5. TSH and Thyroglobulin total and antibody will be drawn on Days 5 of Weeks 1 and 5 (i.e., the weeks that the ^{124}I PET/CT are to be performed). TSH and Free T4 will be drawn for the Week 3 assessment (thyroglobulin and thyroglobulin antibodies are not required to be drawn during this week).
- m: The same modality (echocardiogram or MUGA) should be used at baseline and at follow-up.
- n: Ophthalmology exams should be obtained at baseline, and if clinically indicated, during study. Ophthalmology exam should include Ocular Coherence Tomography, fundoscopy, tonometry, visual field examination, and corrected visual acuity assessments.
- o: For the research blood specimen, approximately 10 mL of blood will be collected in a tube with EDTA (usually lavender top) any time after the informed consent has been signed.

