Study Calendar for PATIENTS WHO RECEIVE RAI (Week 5, Day 6 and beyond)

If the second lesional dosimetry with trametinib reveals sufficient tumoral iodine incorporation to deliver a dose of $\geq 2,000$ cGy with ≤ 300 mCi of RAI, then the patient will continue on trametinib and a low iodine diet (as decided by the treating physician(s)). The schedule of treatments and assessments for these patients are detailed below (NOTE: Week and day number designations may change if there are interruptions in study treatments/assessments):

	Wk 5	Wks 6 & 7 D6 & D7	5 weeks (+/- 2 weeks) after RAI therapy	About 3 or 4 months after RAI	About 6 months after RAI (+/- 1 week)
Trametinib ^a	X	X			
Adherence to low iodine diet ^a	X	X			
Whole body and blood dosimetry and ^{131}I (RAI) treatment with Thyrogen stimulation (per standard of care) ^a		X			
Concurrent meds	X-----X				
Physical exam			X		
Vital signs			X		
Weight			X		
Performance status			X		
CBC w/diff, plts			X		
chemistry ^b			X		
TSH, free T4, thyroglobulin, thyroglobulin antibody			X	X	X
beta-HCG		X ^c			
Echocardiogram or MUGA ^c			X ^c		
Adverse event evaluation	X-----X (Monitored for 30 days following the last dose of trametinib.)				
Radiologic evaluation (CT(s) and/or MRI(s)) for tumor measurements NO IODINATED CONTRAST IS ALLOWED	X ^d			X ^d	X ^d

a: Patients will be continued on trametinib and a low iodine diet. Whole body and blood dosimetry and thyrogen-stimulated ^{131}I (RAI) treatment is to be completed no later than in Week 7 (unless changes/interruptions of study drug administration and/or study assessments had to be enacted such that whole body and blood dosimetry and therapeutic RAI has to be completed after Week 7)(this dosimetry will be conducted as per institutional guidelines). Trametinib will be continued through 2 days after therapeutic ^{131}I administration. The low iodine diet will be continued through 1 day after ^{131}I treatment. ^{131}I therapeutic dosing will be guided by the dosimetric determination of the maximum tolerated activity (MTA): the ^{131}I activity administered concomitantly with trametinib is not to exceed the MTA plus 3 mCi (i.e., $[\text{MTA}] \leq [\text{MTA} + 3 \text{ mCi}]$). **Delays in performing the whole body and blood dosimetry and RAI treatment due to holidays, scheduling conflicts, or interruptions in trametinib therapy may be allowed after discussion with the MSK Principal Investigator.**

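### The thyroglobulin test in Section 13.4 ignores the thyroglobulin antibody that the trial already draws, so a change in assay interference could create a false fall or hide a real one

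*Combined protocol and SAP*

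**What the plan says.** Section 13.4 states the aim for Cohorts A and B in the same words: "the goal will be to determine whether treatment with trametinib and RAI is accompanied by decrease in thyroglobulin". The method is that "we will perform a Wilcoxon signed rank test for paired samples to compare the thyroglobulin level before and after RAI treatment", and the analysis set is given only as "in the subset of patients treated with RAI". The Cohort C text repeats the test. None of the three gives an exclusion, stratification or sensitivity analysis based on antibody status. Section 13.4 also states no alpha, sidedness or power for this test.

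The antibody is nevertheless collected throughout (Section 10):

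- **Before RAI, Day 1:** note l to the first calendar says "TSH, free T4, thyroglobulin, and thyroglobulin antibody will be drawn on Day 1 of weeks 1 and 5", preferably before that day's Thyrogen.
- **Before RAI, Day 5:** the same note says "TSH and Thyroglobulin total and antibody will be drawn on Days 5 of Weeks 1 and 5", which is after the Thyrogen injections on Days 1 and 2.
- **After RAI:** the calendar row "TSH, free T4, thyroglobulin, thyroglobulin antibody" is marked at about 5 weeks, 3 to 4 months and 6 months.
- **Cohort C:** both are checked about every two cycles.

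Note l requires neither thyroglobulin nor antibody on Day 3 or in Week 3, so wherever thyroglobulin is required the antibody is too. The eligibility criteria (Sections 3.1 and 3.2) do not mention the antibody.

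**The concern.** A change in thyroglobulin is a listed secondary objective for each cohort (Section 1.2). Section 2.4 calls thyroglobulin a thyroid tumor marker and reports substantial falls in all 8 RAI-treated pilot patients, so a positive test here is likely to be read as evidence of activity. There is no control arm in which a measurement artefact would show up.

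If the antibody interferes with the assay, the measured value in an antibody-positive patient mixes tumor thyroglobulin with interference. A paired test removes only the part that is the same at both draws. If interference changes after RAI, the pair carries an artefact. A false fall pushes the test towards a claimed decrease, and a false rise works against a real one. The sets are small (at most 25 patients in Cohort A and 10 in Cohort B, Section 13.2), so a few such pairs could change the result. Without a rule written in advance, antibody-positive patients would be handled after the values are known.

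**Working it through.** The plan gives no figure for this test, so there is nothing to reproduce. The question is how far antibody-related artefacts could move its error rate.

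**Inputs from the documents.** Paired signed rank test; RAI-treated patients only; at most 25 (Cohort A) and 10 (Cohort B).

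**Assumptions, none of them in the documents.** Exact two-sided test at 0.05. The after-minus-before difference for patient *i*, in SD units, is

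Dᵢ = Zᵢ + Aᵢ·Sᵢ·δ

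Here Zᵢ is standard normal (no true change) and Aᵢ = 1 with probability *f* (patient affected). Sᵢ = −1 (artefactual fall) with probability *q* and +1 otherwise, and δ is the artefact size. A false decrease is a rejection in the direction of a fall. There were 40,000 simulated trials per setting.

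**Result for 15 pairs, f = 20%**

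| Artefact pattern | False-decrease rate |
|---|---|
| No artefact | 0.024 |
| Falls and rises equally likely, δ = 1 or 3 | 0.024 |
| Two-thirds falls, δ = 3 | 0.05 |
| All falls, δ = 1 | 0.09 |
| All falls, δ = 3 | 0.19 |

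**Fixed number affected, all falls.** With exactly 3 of 15 affected, the rate is 0.078 at δ = 1 and 0.144 at δ = 3. With 2 of 25 it is 0.045 to 0.069, and with 5 of 25 it is 0.115 to 0.268. Leaving out the affected patients brings it back to about 0.02 in each case.

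**Opposite direction.** With 20 pairs, a true fall of 0.8 SD and 10% of patients showing artefactual rises of 3 SD, power drops from 0.91 to about 0.45.

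**Cost of exclusion in small sets.** The smallest two-sided p with *n* untied pairs is 2/2ⁿ. For n = 5 this is 2/32 = 0.0625, and for n = 6 it is 2/64 = 0.031. Five or fewer pairs therefore cannot reach 0.05. In the pilot (Section 2.4, Table 1), 1 of 3 wild-type patients received RAI. If that share held in Cohort B, an assumption resting on three patients and another drug, there would be about 10 × 1/3 ≈ 3 pairs.

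**The case against.** The strongest objection is that the premise comes from outside the documents. No section says that the antibody interferes with the assay, and the assay type, antibody-positive share and direction of any artefact are all missing. This stands. Interference is used here as general assay knowledge, and every rate above is conditional on it.

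A reader might infer that the test is biased towards a false decrease. The documents do not support that. Nothing in them favours falls over rises, and with equal shares the false-decrease rate does not move. The highest rates need every artefact to be a large fall.

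A reader might also infer that the artefact reaches the response endpoint, because Section 11.1.4.2 requires an elevated tumor marker to normalize for complete response. That section does not name thyroglobulin. In any case the Cohort A rule counts complete and partial responses together, and Section 11.1.4.3 classes a patient with target lesions gone and non-target status short of complete response as a partial response.

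Nor does the test take every patient ever given RAI. For those treated after a third scan, "that data will not be included in the statistical analyses for Cohorts A and B, but kept separate for this exploratory analysis".

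Two objections bear on the remedy. Requiring a negative antibody after RAI selects on a post-treatment value. Section 13.5.2 also wants conclusions based on all eligible patients. That text concerns response and does not bar a validity rule for a laboratory marker, but it is a good reason to keep the all-patient result in view.

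**Conclusion.** The concern holds as a gap in a stated analysis. The plan collects the antibody whenever it requires thyroglobulin, then tests thyroglobulin without using it. The consequence is possible but not shown to be likely. It needs interference that differs between the two draws, in enough patients, and mostly in one direction for a false decrease.

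Under the stated assumptions (15 pairs, 20% affected) the false-decrease rate runs from no inflation to about eight times its nominal value (0.19/0.024 ≈ 8). Artefactual rises would cost power instead. For Cohort B a false-positive test may not arise at all, because too few pairs may remain to reach significance.

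This is a supportive secondary analysis. The decision rules in Section 13.1 rest on 6-month progression-free status and response (Cohort A) and on predicted lesional dose (Cohort B), and they do not change.

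**What to change.** Amend Section 13.4 as follows.

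1. Name the before and after draws, and choose a pair in the same TSH-stimulation state. The calendars offer several draws, some after Thyrogen and some not; TSH is drawn at each, so the match can be checked.
2. Define antibody positivity by assay and cutoff.
3. For Cohorts A and B, report the signed rank test in RAI-treated patients who are antibody-negative at both draws, next to the result in all RAI-treated patients of the cohort.
4. List antibody-positive patients individually, with thyroglobulin and antibody values over time.
5. State that selection on the post-RAI antibody is a limitation, and show the set that is antibody-negative at baseline as a check.
6. Where five or fewer pairs remain, describe the data and do not test.
7. Apply the same antibody rule to the Cohort C thyroglobulin analysis.

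This needs a short paragraph and no new samples. The cost is fewer pairs in the restricted analysis, which matters most in Cohort B.

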1.2 Secondary Objectives

For Cohort A (RAS MUT thyroid cancer patients):

- 1) To determine the proportion of patients following trametinib therapy with increased tumoral iodine incorporation as quantified with ^{124}I PET/CT lesional dosimetry.
- 2) To evaluate the safety/tolerability of trametinib with or without RAI.
- 3) To evaluate changes in thyroglobulin levels in patients treated with RAI.
- 4) (Exploratory) To explore potential correlations between genomic alterations present in the tumor and/or tumoral pharmacodynamic changes induced by trametinib to clinical outcomes.

For Cohort B (BRAF/RAS WT thyroid cancer):

- 1) To evaluate the effect of trametinib on enhancing RAI activity by determining the ORR at 6 months following treatment with RAI in co-administration with trametinib.
- 2) To evaluate the effect of trametinib on enhancing RAI activity by determining the proportion of patients alive at 6 months without disease progression by RECIST v1.1 criteria following treatment with RAI in co-administration with trametinib.
- 3) To evaluate the safety/tolerability of trametinib with or without RAI.
- 4) To evaluate changes in thyroglobulin levels in patients treated with RAI.
- 5) (Exploratory) To explore potential correlations between genomic alterations present in the

tumor and/or tumoral pharmacodynamic changes induced by trametinib to clinical outcomes.

For Cohort C (select patients from Cohorts A and B with insufficient ¹²⁴I PET changes):

- 1) *(Exploratory)* Preliminary evaluation of best objective response (BOR) rate for patients treated with trametinib alone.
- 2) *(Exploratory)* Preliminary evaluation of the proportion of patients following treatment with trametinib alive at 6 months without disease progression by RECIST v1.1 criteria.
- 3) To evaluate the safety/tolerability of trametinib.
- 4) To evaluate changes in thyroglobulin levels in patients treated with trametinib.
- 5) *(Exploratory)* To explore potential correlations between genomic alterations present in the tumor and/or tumoral pharmacodynamic changes induced by trametinib to clinical outcomes.
- 6) *(Exploratory)* To explore the impact of continued trametinib upon RAI avidity and efficacy.

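### Cohort C thyroglobulin: the only test named compares values before and after RAI, so the objective of change on trametinib has a stated intention but no matching test

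*Combined protocol and SAP*

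**What the plan says.** Section 1.2 gives Cohorts A and B a thyroglobulin objective tied to RAI treatment. Cohort C has a different one; item 4 reads "To evaluate changes in thyroglobulin levels in patients treated with trametinib". It is not labelled exploratory, although items 1, 2, 5 and 6 of the Cohort C list are.

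Section 13.4 describes Cohort C as patients whose second lesional dosimetry does not lead to RAI: "Such patients may be continued on trametinib alone in Cohort C", subject to the physician's judgement and the patient's agreement. Its expected size is "approximately 10 patients in total from Cohorts A and B will be enrolled in Cohort C".

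The Cohort C thyroglobulin paragraph has two clauses. The first is "Changes in thyroglobulin will also be assessed while on treatment with trametinib". After a semicolon comes a paired Wilcoxon signed rank test, described with the words "compare the thyroglobulin level before and after RAI treatment in the subset of patients treated with RAI". Cohorts A and B have the same test, and there it serves a stated purpose: "the goal will be to determine whether treatment with trametinib and RAI is accompanied by decrease in thyroglobulin".

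The last paragraph of Section 13.4 deals with Cohort C patients who have a third 124I scan: "These patients will have the same Cohort A and B primary/secondary endpoints evaluated in an exploratory manner". Data from those who then receive 131I are kept apart from the Cohort A and B analyses. This corresponds to exploratory item 6, "To explore the impact of continued trametinib upon RAI avidity and efficacy".

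**The concern.** The objective and the test ask different questions in different patients. The objective concerns everyone in Cohort C and the effect of trametinib. The test concerns only RAI-treated patients and the change across RAI, and by design Cohort C does not receive RAI on entry. The test clause repeats the Cohort A and B text and has no main verb, which suggests it was carried over.

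Followed as written, the named test cannot answer objective 4. The analyst would then have to choose the baseline draw, the on-treatment draw and the summary measure once the data are in hand. The available draws differ in time on drug and in Thyrogen exposure, so in about 10 patients that choice could affect what is reported.

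**Working it through.** No stated figure is in dispute. The check compares the texts and then uses the study calendars.

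**1. Objective against test**

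| Cohort | Objective (Section 1.2) | Test (Section 13.4) | Match |
|---|---|---|---|
| A | Change in RAI-treated patients | Before vs after RAI, RAI-treated subset | Yes |
| B | Change in RAI-treated patients | Same | Yes |
| C | Change in trametinib-treated patients | Same | No |

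**2. Who enters the Cohort C test.** A Cohort C patient can reach 131I only through the optional third scan (Sections 5.1.1, 10 and 13.4). Call that number k. The documents do not give k; it can be anything from 0 to about 10. At k = 0 the test cannot be run.

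**3. What the test measures in those k patients.** They follow the Section 10 calendar for patients who receive RAI.
- Last trametinib dose: 2 days after 131I (footnote a).
- First scheduled post-RAI thyroglobulin: 5 weeks +/- 2 weeks, so 35 - 14 = 21 to 35 + 14 = 49 days after RAI.
- Time off trametinib at that draw: 21 - 2 = 19 to 49 - 2 = 47 days.

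The first scheduled post-RAI value therefore follows both 131I and drug withdrawal. Later post-RAI draws, at about 3 to 4 and 6 months, are further still from the last dose.

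**4. Whether a matching comparison is possible with scheduled draws.** Take Week 1 Day 1 as day 1; trametinib starts on Week 1 Day 6, day 6.
- Week 1 Day 1: before trametinib, and preferably before that day's Thyrogen (footnote l of the first calendar).
- Week 5 Day 1: day 29, which is 29 - 6 = 23 days after starting.
- First draw from Cycle 3. The calendar for patients not receiving RAI starts Cycle 2 after Week 5, on day 36, so Cycle 3 Week 1 Day 1 is 36 + 28 = day 64, or 64 - 6 = 58 days after starting. If footnote b's 8 weeks +/- 1 week is instead counted from the Week 5 draws (day 29 or 33), the range is 29 + 49 = day 78 to 33 + 63 = day 96, or 72 to 90 days after starting.

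The samples exist. What is missing is a statement of which pair is compared and how the change is summarised.

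**5. A complication for the on-trametinib draw.** A third scan is allowed 4 weeks or more after the second scan process ends on Week 5 Day 5 (day 33), so from about 33 + 28 = day 61. That can precede the Cycle 3 draw on either reading. The third scan is Thyrogen-stimulated, so the comparison must be limited to values taken before it.

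**The case against.** The best defence is that the semicolon separates two analyses: an assessment of change on trametinib for the whole cohort, and a signed rank test for any patients who later receive RAI. Objective 4 asks only for changes to be evaluated and promises no test, so on this reading nothing is contradictory.

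Part of this stands. The first clause does commit to assessing change on trametinib, and a descriptive report would honour it. But the reading does not repair the plan. Objective 4 would have no test, baseline, time point or summary, and the RAI test would duplicate the separate exploratory analysis of third-scan patients.

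A second objection is that Cohorts A and B also say only before and after RAI, with three post-RAI draws scheduled and none named. That is true, and naming the draw there would help as well. The difference is that in those cohorts the contrast and the patients fit the objective; in Cohort C they do not.

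A reader might go further and infer that objective 4 has no analysis at all, or that the test is empty by construction. The first clause rules out the former and the third-scan route the latter. A reader might also argue that the RAI-treated subset is too small to reach significance. That needs k, a significance level and a choice between one- and two-sided testing; the plan states none of these for thyroglobulin.

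**Conclusion.** The point holds as a mismatch between one secondary objective and its only named test. The plan states an intention for Cohort C objective 4 but specifies no test that fits it. The named test reaches 0 of about 10 patients, or k of about 10 if k receive late 131I, and in those k its first scheduled post-RAI value falls 19 to 47 days after the last trametinib dose.

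This rests on the calendars being followed as scheduled and on the estimated cohort size. It is a minor correction: a descriptive report remains possible, the plan makes no power claim for thyroglobulin, and no primary endpoint or decision rule changes.

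**What to change.** In the Cohort C paragraph of Section 13.4, keep the opening clause and replace the test clause with text along these lines:

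> Change in thyroglobulin on trametinib will be analysed with a paired Wilcoxon signed rank test, reported with the median change, from the Week 1 Day 1 value (before trametinib) to one pre-named on-trametinib draw (for example, the first scheduled from Cycle 3), in all Cohort C patients with both values. Only values taken before any third-scan Thyrogen and before any 131I are used. The number of patients without a pair is reported. The change to Week 5 Day 1 is given as supportive.

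The text should also state:
- whether the test is one- or two-sided; objective 4 names no direction, so two-sided fits it;
- whether patients positive for thyroglobulin antibody are included, for example included, with a sensitivity analysis that excludes them.

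Drop the before/after-RAI test from Cohort C. The last paragraph of Section 13.4 already carries the Cohort A and B endpoints into the separate exploratory analysis of third-scan patients.

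The cost is a text edit, with no new visits or samples. The downside is lost pairs: the calendar for patients not receiving RAI marks no thyroglobulin in Cycle 2 or at Off Study, so early discontinuation, or a third scan before the Cycle 3 draw, may leave fewer than about 10. The documents do not allow that loss to be estimated. The Week 5 Day 1 change softens it but reflects only about 3 weeks on drug.
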